## 72.4 Adverse Events of Special Interest (AESI)

Certain AEs may require additional investigation to ensure appropriate information and data are captured to appropriately evaluate the clinical development of VC-02. These are considered adverse events of special interest (AESI) and may include but are not limited to:

- AEs leading to the unexpected or premature explantation of VC-02-300 or sentinel units.
- AEs that result in early withdrawal from the study.
- Severe hypoglycemic events occurring after VC-02 implantation possibly or definitely related to VC-02.

If an AESI occurs, the Sponsor may request that additional data be collected for these events.

## 725 Serious Adverse Events

An SAE is any untoward medical occurrence meeting at least one of the following criteria:

- Results in death;
- Is life-threatening (immediate risk of death);
- Requires in-patient hospitalization or prolongation of existing hospitalization;
- Results in persistent or significant disability/incapacity (substantial disruption of the ability to conduct normal life functions);
- Results in congenital anomaly/birth defect;
- Constitutes an Important Medical Event in the opinion of the Investigator and/or Sponsor.

Medical and scientific judgment is exercised in determining whether an event is an important medical event. An important medical event may not be immediately life threatening and/or result in death or hospitalization. However, if it is determined the event may jeopardize the subject or may require intervention to prevent one of the other SAE criteria, the important medical event should be reported as serious.

Based on the definition above, SHE may or may not be reported as SAEs and will be classified at the Investigator's discretion. In all instances, SHEs are to be recorded on the HE eCRF.

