#### 1.4.1. Potential Risks

Some of the potential risks for study participation are hypothetical at this stage of VC-02 development. There are safety-related, strictly-defined discontinuation and explant rules noted in Section 8.5. Potential risks include, but are not limited to the below items.

- There are inherent surgical risks with the implantation and explantation of VC-02 units including pain, bleeding, hematoma, seroma, tenderness, redness, scarring, and infection. Steps will be taken to minimize the risks and to make the subject comfortable during the procedure with anesthetic and post-procedure analgesia.
- With any implanted product, the possibility of migration or extrusion of the implant exists, along with the need for explantation.

- The use of anesthesia itself may cause side effects. The type(s) of anesthesia used during the implantation and explantation procedures will be determined by the Investigator or Surgeon. Side effects may include, but are not limited to:
  - Local Anesthesia: Stinging and/or a burning sensation. Less likely side effects include nausea, vomiting, dizziness, drowsiness, allergic reactions (e.g., redness, itching, and rash), low blood pressure, weakness, severe numbness or tingling, ringing in ears, blurry or double vision, slurred speech, metallic taste in mouth, mental status change, muscle twitching, and seizures.
  - *General Anesthesia*: Harm to the vocal cords, heart attack, lung infection, stroke, trauma to the teeth or tongue, or temporary mental confusion. Rarely, waking during anesthesia or death may occur.
  - Conscious Sedation: Difficulty breathing.
- After implant of VC-02, there may be an increased risk of HEs. Although the risk of HEs from grafted units is minimal based upon nonclinical results, as the implanted cells begin producing insulin, subjects and investigators need to monitor blood sugar levels closely and adjust the amount of required exogenous insulin.

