# 8.5. Study Stopping Rules

If any of the following safety events are noted to occur in the study, an ad-hoc meeting of the DSMB will be requested. The DSMB will review the data and will recommend stopping the study for any of the following:

- 1. Two or more subjects have pronounced immune responses to VC-02.
- 2. Two or more subjects experiencing a NCI-CTCAE Grade 3 (severe) treatment emergent adverse event (TEAE) in the same Medical Dictionary for Regulatory Activities (MedDRA) system organ class (SOC) and preferred term (PT) considered to be possibly or probably related to the investigational product. TEAE is defined as an AE that starts on or after the date of implant surgery.
- 3. After a minimum of eight weeks post-implantation, there are two or more subjects who each experience two or more Severe Hypoglycemic Events (SHE) over a 6-month period unrelated to anything other than VC-02. This assumes the SHE occurred despite reasonable adjustments in the exogenous insulin requirements and appropriate dietary adjustments.
- 4. Two or more subjects develop SAEs deemed related to the implantation of VC-02 itself; examples of such events are noted below:
  - a. Development of an off-target cell growth (i.e., teratoma) within the unit which is noted on ultrasound and confirmed by pathologist.
  - b. A related, severe, persistent, inflammatory response that does not resolve (e.g., severe site reactions, urticaria, erythematous rash, anaphylaxis, acute respiratory insufficiency, swelling).
- 5. Two or more subjects have an unexplained graft malfunction requiring explant.

In addition to these events, the DSMB can consider recommending a temporary delay or hold on enrollment in the trial for events considered by the Investigator to be related to VC-02. The DSMB can also recommend treatment continue for a shorter duration (i.e., less than the planned two years) or with a fewer number of implanted units. The DSMB can also recommend the Sponsor close the study at any time in response to any legitimate safety concerns. The Sponsor will communicate DSMB recommendations to each site in a timely fashion. Each site's Ethics Committee will make the ultimate decision to delay enrollment, modify treatment duration, or stop the study based on DSMB recommendations.

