#### 4.2 Analysis Sets

The Full Analysis Set (FAS) is the intent-to-treat (ITT) set of subjects. This set is defined as all subjects who were enrolled into VC02-101 and received implantation of at least one VC-02-300 or sentinel unit on Study Day 1. Note that Cohort 1 in VC02-101 and in VC02-102 have no efficacy endpoints, so the subjects from Cohort 1 in VC02-101 and VC02-102 are not included in the FAS. All Cohort 2 VC02-101 efficacy summaries/analyses will be performed on the FAS. Subjects will be summarized by treatment group.

The Safety Analysis Set (SAS) will include all subjects from Cohort 1 and Cohort 2 who were enrolled into VC02-101 or VC02-102 and in whom an implant surgery was attempted, regardless of whether any VC-02-300 units or sentinel-sized units were actually implanted. The SAS will be used for safety summaries. All subjects enrolled in Protocol VC02-102 are part of Cohort 1.

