#### 4.6 Data Derivations and Transformations

All data derivations are for efficacy data. Therefore, information in this section pertain only to Protocol VC02-101.

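### No severe-hypoglycemia or AESI safety table is planned, and the severe-event analyses with a defined window cover only Cohort 2, from Day 99 or Week 16

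*SAP*

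**What the plan says.** **Recording.** Protocol 7.10.4 defines an SHE by the need for another person's active help. Seriousness is a matter of judgment: "SHE may or may not be reported as SAEs and will be classified at the Investigator's discretion" (SAP 7.2.5; Protocol 8.2 agrees). The hypoglycemia form is not optional: "In all instances, SHEs are to be recorded on the HE eCRF".

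**Safety role.** Protocol 1.4.1 states "After implant of VC-02, there may be an increased risk of HEs". The AESI list in SAP 7.2.4 includes "Severe hypoglycemic events occurring after VC-02 implantation possibly or definitely related to VC-02". Under Protocol 8.5, item 3, the stopping rule is met if, after the first eight weeks, "there are two or more subjects who each experience two or more Severe Hypoglycemic Events (SHE) over a 6-month period". The rule counts only events attributed to VC-02 and is not limited to one cohort. Protocol 13.6 has a similar criterion for withdrawing a subject.

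**Analysis.** SAP 4.6, which holds the hypoglycemia derivations, opens with "All data derivations are for efficacy data" and limits itself to VC02-101. On the Full Analysis Set, SAP 4.2 says "so the subjects from Cohort 1 in VC02-101 and VC02-102 are not included in the FAS". SAP 6.2 runs every secondary efficacy analysis on that set. SAP 4.6.3 takes diary frequency from the 14 days before the visits at Weeks 16, 26, 39, 52, 78 and 104. SAP 6.2 analyses freedom from SHEs in intervals from Week 16 to Week 104.

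**Safety section.** SAP 7.2.7 lists 18 TEAE and TESAE displays (i to xviii). SAP 7.6 adds off-target growth, immune sensitization and implant tolerability. None is an SHE table or an AESI table. Protocol 10.4.3 and 10.4.5.2 do not plan one either.

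**The concern.** The trial treats severe hypoglycemia as a safety matter when it watches subjects, and mainly as an efficacy outcome when it reports them. This is a first-in-human trial in which the Cohort 1 primary endpoint is a safety profile. Yet the only form that must hold every SHE feeds derivations that exclude Cohort 1 by their analysis set and most of early Cohort 2 by their window.

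Starting at Week 16 is sensible for a benefit question, because the graft needs time to mature. It is not sensible for a harm question. The stopping rule is already counting from Week 8. Protocol 1.2 puts the earliest glucose-responsive activity in nonclinical work at three to four months, so the last weeks before Week 16 fall in or near that period.

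A reader of the safety section would therefore not find how many subjects had an assistance-requiring event, or at what rate, in either cohort or overall.

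**Working it through.** The plan states no figure on this point, so there is none to reproduce. The check has three parts.

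**1. When the windowed analyses start.** The target day is 7 × week + 1.
- Week 16: 7 × 16 + 1 = Day 113, which matches the target day in SAP 4.3. The 14 days before it are Days 99 to 112, so diary frequency starts 14 weeks after implant.
- Week 8: 7 × 8 + 1 = Day 57. The stopping rule starts here, 16 − 8 = 8 weeks before the first SHE-free interval.
- The diary windows total 6 × 14 = 84 days of 104 × 7 = 728 (11.5%). SAP 6.2 lists only Weeks 16, 26, 52 and 78 for the frequency analysis: 4 × 14 = 56 days (7.7%).

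**2. Follow-up outside the SHE-free analyses.** Inputs: Cohort 1 has 3 to 15 subjects and Cohort 2 up to 60 (Protocol 4.1), with 104 weeks of implantation. Assumption: Cohort 2 fills and every subject completes 104 weeks. VC02-102 is not counted.

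Left out = (Cohort 1 n × 104) + (60 × 16). Total = (Cohort 1 n + 60) × 104.

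| Cohort 1 n | Left out (subject-weeks) | Total | Share |
|---|---|---|---|
| 15 | 1,560 + 960 = 2,520 | 75 × 104 = 7,800 | 32.3% |
| 3 | 312 + 960 = 1,272 | 63 × 104 = 6,552 | 19.4% |

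Within Cohort 2 alone the share is 16/104 = 15.4%.

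**3. Where else an SHE could appear.**

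| Place | Cohort 1 | Cohort 2 before Week 16 | Separates assistance-requiring events? |
|---|---|---|---|
| TEAE tables, SAP 7.2.7 | If reported as an AE | If reported as an AE | No; by SOC, PT, grade and relationship |
| Hypoglycemia listing, SAP 6.2 | Not stated; sits in the efficacy section | Yes | A listing, not a table |
| Severe-event sentence, SAP 4.6.7 | Not stated; the section concerns Cohort 2 CGM | No window given | Yes, but no analysis set or table |
| CGM episodes, SAP 4.6.4 | No | Yes, 14 days before each scheduled visit | No; severe there means below 54 mg/dL |

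The combined related category in SAP 7.2.3 includes events rated Unlikely Related. The tables built on it therefore cannot isolate the AESI, which is limited to possibly or definitely related events.

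Some early Cohort 2 diary events can also enter as baseline, because SAP 4.6.3 fills a short baseline with data from Day 4 onward. With the minimum two-week gap in Protocol 6.2 and Visit 2 at Day −14, Days −14 to −3 give 12 days. Removing the MMTT day leaves 11. The other 28 − 11 = 17 days come from Days 4 to 20.

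**The case against.** The best defence is that no data are lost. The Investigator's discretion concerns SAE status, not AE reporting. Protocol 8.1 defines an AE broadly and requires all observed or volunteered AEs to be reported, and an assistance-requiring event fits that definition. Once reported as an AE, it enters the safety-set tables for both cohorts from Day 1. Display iv breaks TEAEs down by relationship to product, so possibly or definitely related hypoglycemia can be read there without the combined category. Two other AESI categories are partly shown elsewhere: withdrawals in display xviii, and premature VC-02-300 explants with reasons in SAP 7.1.

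Most of this stands, and it rules out several stronger readings that a reader might infer:

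- *That severe hypoglycemia is summarized only as efficacy, or that Cohort 1 events are wholly omitted.* The TEAE tables and the listing are against this. What remains is that no passage expressly requires every SHE to go on the AE form as well, and that SOC and PT tables do not separate assistance-requiring events from other hypoglycemia.
- *That nothing is summarized before Week 14.* SAP 4.6.7 promises a severe-event summary with no start week. Because it names no window, set or table, it cannot be relied on to fill the gap.
- *That the stopping rule cannot work.* The rule counts only repeated events attributed to VC-02, despite insulin and dietary adjustment. It runs through diary review, Sponsor review and DSMB meetings (Protocol 7.10, 8.4 and 8.5). The DSMB Charter is not among the documents and may specify SHE outputs.
- *That a given number of events would be missed.* The documents give no SHE rate, so any count would rest on an unsourced figure.

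Protocol 1.4.1 also names hypoglycemic events in general, not severe ones, and calls the graft-related risk minimal on nonclinical evidence.

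**Conclusion.** The point holds as a reporting gap. No dedicated SHE or AESI safety table is planned. The SHE analyses with a defined window are Cohort 2 efficacy analyses, from Day 99 for diary frequency and from Week 16 for freedom from SHEs. The gap comes from stated analysis-set and window rules, so it is more than missing detail.

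Its size is 32% of planned VC02-101 subject-weeks outside the SHE-free analyses at maximum enrolment, or 19% with three Cohort 1 subjects. Both figures assume that Cohort 2 fills and that follow-up is complete. They measure follow-up outside those analyses, not events lost. The change is worth making because the trial is first-in-human, the event is a stopping criterion and the cost is small.

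**What to change.** In SAP 7, add two tables on the Safety Analysis Set.

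1. **SHE table from the hypoglycemia eCRF**, using the protocol's assistance-required definition rather than the CGM threshold. Show subjects with at least one SHE, number of SHEs and SHEs per patient-year, from Day 1 to final explant, by cohort and treatment group, split at Week 8 and Week 16.
2. **AESI table beside it**, showing SHEs assessed as possibly or definitely related to VC-02, without the combined category that includes Unlikely Related. The stopping rule concerns attributed events, so a crude rate alone would not show what it acts on. Causality is documented for AEs, so a row counting eCRF SHEs with no matching AE record would show how complete this table is.

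Give the SAP 4.6.7 severe-event summary an analysis set and window, or refer it to the first table.

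The cost is two extra tables from data already collected. Visits, forms and clinical procedures do not change.

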## 72.6 Suspected, Unexpected Serious Adverse Reactions (SUSAR)

A SUSAR is a serious adverse reaction which is thought to be causally related to the investigational

CONFIDENTIAL

product, surgical procedure, and/or immunosuppression regimen and which is unexpected to occur.

Because of the limited shelf-life of the investigational product, the results of the 14-day sterility testing of VC-02 are not available until after implantation occurs. In the unexpected event of positive culture results from this test, the Sponsor will notify the Investigator, who will then notify the subject. The Sponsor will initiate further testing of the positive sample to identify the microorganism and conduct a root-cause analysis. The Investigator and Sponsor will evaluate any additional actions required to appropriately monitor the subject based on the results of the sample. If the medical condition of the subject is impacted as a consequence of the microorganism causing the positive sterility results, the event should be reported as a SUSAR.

#### 72.7 Adverse Event Summaries

All AEs (serious and nonserious) occurring after completion of the informed consent process and before the end of study, regardless of relationship to study drug, will be included and classified by SOC and PT using MedDRA.

For TEAEs, the following will be summarized and presented for the SAS:

- i. An overall summary of TEAEs, which includes:
  - a. the number and percentage of subjects experiencing a TEAE
  - b. the number and percentage of subjects experiencing a TEAE by toxicity grade
  - c. the number and percentage of subjects experiencing a TEAE by relationship to VC-02 combination product
  - d. the number and percentage of subjects experiencing a TEAE by relationship to the surgical procedures required for VC-02 administration
  - e. the number and percentage of subjects experiencing a TEAE by relationship to the immunosuppressive drug regimen
  - f. the number and percentage of subjects experiencing a TEAE leading to study withdrawal
  - g. the number and percentage of subjects experiencing a treatment emergent SAE (TESAE)
  - h. the number and percentage of subjects experiencing a TESAE by toxicity grade
  - i. the number and percentage of subjects experiencing a TESAE by relationship to VC-02 combination product
  - j. the number and percentage of subjects experiencing a TESAE by relationship to the surgical procedures required for VC-02 administration
  - k. the number and percentage of subjects experiencing a TESAE by relationship to the immunosuppressive drug regimen
- ii. the number and percentage of subjects experiencing a TEAE by SOC and PT
- iii. the number and percentage of subjects experiencing a TEAE by SOC, PT and toxicity grade

- iv. the number and percentage of subjects experiencing a TEAE by SOC, PT and relationship to investigational product
- v. the number and percentage of subjects experiencing a TEAE by SOC, PT and relationship to the surgical procedures required for VC-02 administration
- vi. the number and percentage of subjects experiencing a TEAE by SOC, PT and relationship to immunosuppressive drug regimen.
- vii. the number and percentage of subjects experiencing a TEAE by SOC, PT and related to investigational product
- viii. the number and percentage of subjects experiencing a TEAE by SOC, PT and related to the surgical procedures required for VC-02 administration
- ix. the number and percentage of subjects experiencing a TEAE by SOC, PT and related to immunosuppressive drug regimen.
- x. the number and percentage of subjects experiencing a TESAE by SOC and PT
- xi. the number and percentage of subjects experiencing a TESAE by SOC, PT and toxicity grade
- xii. the number and percentage of subjects experiencing a TESAE by SOC, PT and relationship to investigational product
- xiii. the number and percentage of subjects experiencing a TESAE by SOC, PT and relationship to the surgical procedures required for VC-02 administration
- xiv. the number and percentage of subjects experiencing a TESAE by SOC, PT and relationship to immunosuppressive drug regimen.
- xv. the number and percentage of subjects experiencing a TESAE by SOC, PT and related to investigational product
- xvi. the number and percentage of subjects experiencing a TESAE by SOC, PT and related to the surgical procedures required for VC-02 administration
- xvii. the number and percentage of subjects experiencing a TESAE by SOC, PT and related to immunosuppressive drug regimen.
- xviii. the number and percentage of subjects experiencing a TEAE leading to study withdrawal by SOC and PT

In the overall summary of TEAEs table (i), besides tabulating the number and percentage of subjects, the total number of TEAE episodes will also be provided. If a subject has repeated episodes of a particular TEAE, all episodes will be counted in the summary table's total number of episodes.

In the remaining summary tables, the incidence of TEAEs will be calculated by dividing the number of subjects who have experienced the event by the total number of subjects in the SAS. Thus, the incidence of TEAEs is shown in terms of the total number of subjects and not in terms of the total number of episodes. If a subject has repeated episodes of a particular TEAE, only one episode per toxicity grade, or one episode per causal relationship, will be counted in the summary tables.

A subject with more than one type of TEAE in a particular SOC will be counted only once in the total of subjects experiencing TEAEs in that particular SOC. Since a subject could have more than one type of TEAE within a particular SOC, the sum of subjects experiencing different TEAEs within the SOC could appear larger than the total number of subjects experiencing TEAEs in that SOC. Similarly, a subject who has experienced a TEAE in more than one SOC will be counted only once in the total number of subjects experiencing AEs in all SOCs.

All occurrences of all AEs will be listed for each subject, grouped by cohort. The listing will contain the following information: treatment group, verbatim term, SOC, PT, toxicity grade, relationship to VC-02 combination product, relationship to the surgical procedures required for VC-02 administration, relationship to the immunosuppressive drug regimen, date and study day of onset, date and study day of resolution, treatment given to treat the adverse event, the outcome, whether the event was an SAE, whether it led to withdrawal and whether it is a TEAE. Listings will be sorted by cohort, treatment group (and within treatment group, the number of sentinels), subject identification number, onset date, SOC, and PT. If the onset date is completely missing, then these events will be presented first. If the onset date is missing a month or a day, then these events will be presented before any complete dates.

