## **10.3.2.** Internal Efficacy and Safety Review

After the last subject in Cohort 2 passes Visit 11 (Week 26), cumulative data from all Cohort 1 and Cohort 2 subjects will be assembled and sent to the DSMB and Sponsor for review. If the Sponsor believes the efficacy data appear robust, and the DSMB believes the safety data are appropriate, the Sponsor may choose to proceed to an End-of-Phase 2 (EoP2) meeting with the FDA to discuss next steps.

The Sponsor will perform a risk/benefit assessment at 9-12 months post-implant for each Cohort 2 subject and at other time points, as warranted. This assessment evaluates each individual subject's data in order to determine whether that subject should continue taking chronic immunosuppression and remain in the study or whether all units will be explanted. Factors evaluated include C-peptide concentration, histology from a sentinel device explanted at approximately nine (9) months, change from baseline in average weekly insulin administration, change from baseline in HbA1c, change from baseline in frequency of hypoglycemic events, change from baseline in Clarke Score, change from baseline in time-in--range, compliance with immunosuppression, as well as adverse events and other safety findings. In cases where a subject is early terminated from the study as a result of the risk/benefit assessment, specific early termination visit procedures (i.e., the 4-hour MMTT and safety ultrasound) will not need to be repeated if they were recently performed (within the last 8 weeks).

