## **13.6.** Reasons for Withdrawal

Investigators will make reasonable efforts to keep enrolled subjects in the study. However, if a subject is removed from treatment, a termination visit must be performed. This would generally include all procedures outlined in Visit 17 (Week 104) as well as the procedures outlined in followup Visit 18 (Week 105). Adverse events should be followed until their resolution.

Subjects may withdraw from the trial at any time at their own request, or they may be withdrawn at any time at the discretion of the Investigator or Sponsor for safety or behavioral reasons.

There are subject-specific criteria and product-related criterion that will necessitate withdrawal from the study.

- After a minimum of eight weeks post-implantation, the subject experiences three or more Severe Hypoglycemic Events (SHE) over a six-month period unrelated to anything other than VC-02. This assumes the SHE occurred despite reasonable adjustments in the exogenous insulin requirements and appropriate dietary adjustments.
- Subject has a new onset, off-target cell growth within the unit confirmed by a board-certified pathologist as a teratoma and is considered related to VC-02.
- Subject appears to mount an immune or inflammatory response that puts the subject at risk for severe or serious immune reaction AEs. In this case, the Sponsor will assess the case fully (e.g., clinically and immune test results) and advise whether an explant of any units is advisable to facilitate continued participation.
- Subject becomes pregnant or in the Investigator's opinion is non-compliant with contraception requirements (see Section 5.4.5).
- Due to the recommendation based upon the outcome of a risk/benefit assessment (see Section 10.3.2).
- Implanted units appear to be damaged or malfunctioning (e.g., localized infections, damaged unit) resulting in severe or serious AEs. Note: In the case of a suspected malfunctioning or damaged unit, the Sponsor will assess the case fully and advise whether an explant of any units is advisable. Explant of one VC-02-300 unit may occur in this situation without requiring the withdrawal of the subject from the study upon request from the Sponsor.

If a subject meets any of these criteria, the VC-02-300 units and any remaining sentinel units will be explanted. The subject will be asked to follow-up with the study site post-explant in the long-term follow-up study.

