#### 4. GENERAL CONSIDERATIONS FOR DATA ANALYSIS

The phrase "treatment group" is used in this section to denote the number of initially implanted VC-02-300 units. If a subject has a VC-02-300 unit explanted for any reason and remains in the study, then he/she will be included in the treatment group that is described by the number of VC-02-300 units originally implanted. If no VC-02-300 units are implanted, but sentinel units are implanted, then the subject will be included in the "0 implanted VC-02-300 units" treatment group. If, during the study, the number of sentinels implanted in subjects who do not have VC-02-300 units varies widely (e.g., one subject has one sentinel unit implanted while another subject has 10 sentinel units implanted), the "zero VC-02-300 unit" treatment group may be further broken out by the number of sentinels implanted.

As the VC02-101 and VC02-102 studies collectively represent the first-in-human trial, there are no statistical hypotheses regarding treatment effects. Rather, displays and comparisons of study results – regarding safety and efficacy among the treatment groups – will primarily utilize descriptive statistics, as noted below.

Unless otherwise specified, continuous variables will be summarized by presenting the number of

non-missing observations, mean, standard deviation, median, minimum, and maximum. Categorical variables will be summarized by presenting the number of subjects and percentage for each category.

Summary results will be provided for each cohort and treatment group as well as overall.

All tabulations will be based on pooled data across centers.

Analyses will be performed using SAS for Windows statistical software, version 9.4 or higher (SAS, Cary, NC), except where other software may be deemed more appropriate.

CTI Clinical Trial and Consulting Services will perform all efficacy and safety statistical analyses.

Subject data will be listed, sorted by protocol, cohort, treatment group (number of VC02-300 units and ascending VC02-20/sentinel units [if applicable]), and subject number.

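### Cohort 2 follow-up for harms can end at 9-12 months after a risk/benefit review, yet adverse events by dose group are summarised only as crude percentages over unequal follow-up

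*SAP*

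**What the plan says.** **Length of follow-up.** Protocol 10.3.2 states: "The Sponsor will perform a risk/benefit assessment at 9-12 months post-implant for each Cohort 2 subject", and at other times as warranted. The purpose is to "determine whether that subject should continue taking chronic immunosuppression and remain in the study or whether all units will be explanted". The inputs are mixed. The text begins "Factors evaluated include C-peptide concentration, histology from a sentinel device explanted at approximately nine (9) months", goes on through insulin use, HbA1c, hypoglycemic events, Clarke score, time in range and immunosuppression compliance, and ends "as well as adverse events and other safety findings". Protocol 13.6 makes the result a withdrawal criterion: "Due to the recommendation based upon the outcome of a risk/benefit assessment". No such review is described for Cohort 1. Otherwise implantation lasts up to two years, with final explant at Week 104.

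**Recording of events.** New AEs are recorded through the subject's last visit (Protocol 8.1.5, SAP 7.2), which SAP 4.3 places 7 days after the last explant. SAEs are reported until 28 days after final explant. Discontinued subjects who have not withdrawn consent move to a separate follow-up study (Protocol 13.6.1, SAP 3.2.4).

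**Summary of events.** SAP 7.2.7 calculates incidence as a simple proportion, "by dividing the number of subjects who have experienced the event by the total number of subjects in the SAS"; table (i) adds episode counts. Protocol 10.4.3 and SAP 4 present the results by treatment group, meaning the number of VC-02-300 units first implanted. SAP 4 foresees "displays and comparisons of study results" on safety and efficacy among these groups, mainly by descriptive statistics. SAP 7.1 summarises duration of exposure and the AE listing gives the study day of onset, but no incidence table uses either.

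**The concern.** A crude percentage compares groups fairly only if they are observed for similar lengths of time. Here the length depends on a decision that uses the subject's own results, and those may vary with dose. A group in which many subjects leave at about Week 39-52 has roughly half the observation time, or less, of a group that stays to Week 104.

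The events at issue are those that keep arising after month 9, such as infection and other effects of continued immunosuppression. Events of implant surgery and induction occur early in everyone.

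This matters because the number of VC-02-300 units is chosen from accumulating data, with the stated intention of using the fewest that work (Protocol 3.2), and safety data feed the decision on an End-of-Phase-2 meeting. A reader of the dose-group columns cannot tell a difference in risk from a difference in follow-up.

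A similar imbalance exists by design in Cohort 1. VC02-102 subjects, with at most four months of implantation, share the Cohort 1 SAS with VC02-101 subjects, who have up to two years.

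**Working it through.** The plan states no AE rate or expected early-explant share, so there is no figure to reproduce. What follows is an illustration.

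**Inputs from the documents.** Review at 9-12 months, taken as Week 39 or 52; full course 104 weeks; Week 26 target is Day 183 (SAP 4.3).

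**Assumptions.** The 104-week risk is 40% and the hazard is the same in both dose groups. Early explant is 80% in one group and 20% in the other. The added week to the last visit is ignored.

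**Step 1, constant hazard.** Risk by week w is 1 − 0.6^(w/104).
- Week 39: 1 − 0.6^0.375 = 17.4%
- Week 52: 1 − 0.6^0.5 = 22.5%

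The group gap is (0.8 − 0.2) × (40% − risk by w).
- Week 39: 0.6 × 22.6 = 13.5 points (21.9% versus 35.5%)
- Week 52: 0.6 × 17.5 = 10.5 points (26.0% versus 36.5%)

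**Step 2, front-loaded hazard.** Let a fraction f of the 104-week cumulative hazard H = −ln 0.6 = 0.511 fall in the first 8 weeks and the rest evenly over the next 96. The share still to come at week w is (1 − f)(104 − w)/96, and the risk by w is 1 − exp[−H(1 − share)].

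| f | w | share to come | risk by w | gap = 0.6 × (40% − risk) |
|---|---|---|---|---|
| 0.5 | 39 | 0.339 | 28.7% | 6.8 points |
| 0.5 | 52 | 0.271 | 31.1% | 5.3 points |
| 0.7 | 39 | 0.203 | 33.4% | 3.9 points |
| 0.7 | 52 | 0.163 | 34.8% | 3.1 points |

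If all the hazard fell before the review, the gap would be zero.

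**Step 3, the opposite direction.** At constant hazard, and if a whole dose group left early (a bound, not an expectation), a truly higher hazard in that group would be hidden up to a ratio of 104/39 = 2.7 or 104/52 = 2.0.

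**Step 4, does a person-time rate repair it?** At constant hazard, yes: both groups give 0.511/104 × 52 × 100 = 25.5 first events per 100 subject-years.

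With front-loading it overcorrects. Take f = 0.5 and w = 39. The weekly hazards are h1 = 0.5 × 0.511/8 = 0.0319 and h2 = 0.5 × 0.511/96 = 0.00266. Mean person-time to first event or to week T is (1 − e^(−8·h1))/h1 + e^(−8·h1)(1 − e^(−h2(T−8)))/h2. This gives 30.1 weeks for T = 39 and 72.7 weeks for T = 104.
- 80% early: 0.309/(0.8 × 30.1 + 0.2 × 72.7) × 5200 = 41.7 per 100 subject-years
- 20% early: 0.377/(0.2 × 30.1 + 0.8 × 72.7) × 5200 = 30.6 per 100 subject-years

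The rate now makes the shorter-followed group look worse, although the hazards are equal. A rate alone is therefore not enough.

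**Step 5, a common early window.** At Week 26 no scheduled review has taken place, so equal hazards give equal figures in both groups. At constant hazard the figure is 1 − 0.6^(26/104) = 12.0% in each. This window cannot show later events, so it complements the rate.

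**Step 6, VC02-102.** Over 16 weeks the same 40% risk at constant hazard would appear as 1 − 0.6^(16/104) = 7.6%.

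**The case against.** The strongest reply is that these tables are descriptive. There is no randomisation and no hypothesis, and dose groups may also differ in device configuration, implant strategy and induction regimen, so exposure adjustment would not make them comparable. Subjects explanted early also have less exposure to the implant, not merely less observation, so the crude incidence under the protocol's own explant policy is a legitimate quantity. Exposure duration by group and day of onset will be reported. All of this stands. It argues for keeping the crude tables and reading any addition descriptively. It does not supply a table that separates risk from follow-up.

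Several stronger readings are tempting, and the documents do not support them:
- **That doses that work will look more harmful.** Adverse events enter the same review, and Protocol 13.6 also withdraws subjects for harm, so a toxic dose may be the one cut short. C-peptide is one factor among several, and the decision is made subject by subject.
- **That the gap is 17-23 points.** The 40% example gives 40 − 22.5 = 17.5 and 40 − 17.4 = 22.6 points only if one dose group is wholly explanted early, the other not at all, and the hazard is constant.
- **That late harms can be seen only in retained subjects.** Withdrawn subjects also undergo explant surgery and the final visits (Protocol 13.6.1). All explanted units go to histology (Protocol 7.9), and later harms can surface in the separate follow-up study. Laboratory data are summarised by visit.
- **That column percentages will be divided by the whole SAS.** SAP 7.2.7 can be read that way literally. SAP 4, however, gives results for each cohort and treatment group, so the column's own number is the ordinary meaning. This is a wording clarification.

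**Conclusion.** The point holds in a limited form. Follow-up for harms in Cohort 2 can be shortened by an outcome-dependent review, and the planned incidence tables by dose group take no account of it. The distortion concerns events that continue to arise after about month 9, and it can run in either direction.

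Under the assumed 40% risk, equal hazards and 80% versus 20% early explant, it is about 10-14 points at constant hazard and about 3-7 points with 50-70% front-loading. It shrinks to nothing if the early-explant shares are similar or the events occur before the review. None of the assumed rates or shares comes from the documents. The descriptive aim makes this an inexpensive improvement to the SAP, not a flaw in a formal comparison. The explant rule itself is not in question.

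**What to change.** In SAP 7.2.7, keep the crude tables. For TEAEs, Grade ≥3 TEAEs, TESAEs and the three related categories (product, surgical procedures, immunosuppression), add by cohort and treatment group:

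1. First-event incidence per 100 subject-years, with person-time from implant to the first event or the end of the applicable reporting period. That end is the last visit for AEs and 28 days after final explant for SAEs.
2. Cumulative incidence to a fixed day before the scheduled review, such as Day 183 (Week 26), using a time-to-event estimate such as Kaplan-Meier so that earlier withdrawals are handled. Week 39 is too late for this purpose: it coincides with the start of the nine-month review and its visit window is ±14 days.

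Show VC02-102 separately from VC02-101 Cohort 1 in these tables. State that any dose-group safety comparison is read from both additions together, descriptively, because the groups are not randomised. State also that the denominator of each percentage is the number of SAS subjects in that column.

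The cost is SAP wording and a few extra tables from dates already collected. The rates assume a roughly constant hazard, which the fixed-day table offsets for the early period.
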